### 9.2.2.2. Supporting graphical analyses

To support the analyses of the primary outcomes, the following graphical methods may be presented additionally:

1. A “waterfall plot”, showing the best percentage change from baseline in the sum of longest diameters of the target lesions, presented as a bar chart. The bars may be coloured to show cohort membership. This analysis may use the subset of patients in the analysis population with baseline tumour size measurement and at least one post-baseline tumour size measurement.
2. A “spider plot”, showing the sum of longest diameters of the target lesions through time, presented as a line chart. Mechanisms will be used to show cohort membership. This analysis will use the subset of patients in the analysis population with baseline tumour size measurement and at least one post-baseline tumour size measurement.
3. A “swimmer plot”, showing time on treatment and the chronological occurrence of responses and progressions, and the durability of responses. This analysis will use the analysis population.

### 9.2.3 Secondary Outcomes

#### 9.2.3.1. Time-to-event outcomes

Time-to-event outcomes (TTP, PFS, OS, DOR, DSD) will be analysed using the Kaplan-Meier method. Median time-to-event (and 90% CIs) will be presented for each outcome. Milestone events rates will be presented (with 90% CIs) for each outcome. Milestone rates will be presented at appropriate times, selecting from 3, 6, 12, 18 and 24 months. Note that 90% confidence intervals are appropriate in this single arm phase II trial. These analyses will use the analysis population; the DoR analysis will use the subset that achieve partial or complete RECIST response.

#### 9.2.3.2. HRQoL outcome

Descriptive longitudinal analyses of each quality of life score will be presented. If appropriate, the EQ5D utility score may be combined with the survival data to estimate quality-adjusted life years using the integrated quality-survival product (Billingham and Abrams 2002). This analysis will use the subset of the analysis population that provide any HRQoL data.

### 9.3 Sample Size Calculations and Operating Characteristics

PePS2 will recruit 60 patients.

#### 9.3.1 Bryant & Day

Being a phase II trial with co-primary efficacy and toxicity outcomes, the original sample size was calculated using a Bryant and Day design. For the toxicity outcome, a cut-off of 10% was selected as the rate below which toxicity would be acceptable and a cut-off of 30% was selected as the rate above which toxicity would be considered unacceptable. A significance level of 5% was selected as the acceptable chance of approving an unacceptably toxic drug as worthy of further investigation.

It was always our intention to treat all PS2 NSCLC patients in PePS2, irrespective of PD-L1 status. However, we knew from [1] that PD-L1 score would affect the efficacy rate. For the purposes of sample size estimation, we estimated that 70% of patients would be PD-L1+ and that, in these patients, an efficacy rate of 30% would be unattractive and a 50% rate would be attractive. In the remaining 30% of PD-L1- patients, we considered that an efficacy rate of 10% would be unattractive and a 20% rate would be attractive. Weighting these efficacy thresholds together yields population thresholds of 24% and 41%. Using a significance level of 10% for the efficacy outcome as the chance of accepting an inactive drug as worthy of further investigation, and overall power of 90%, a Bryant and Day design requires 60 patients and would approve the treatment in the population if no more than 12 toxicities and at least 19 efficacies are observed.

The major flaw in using Bryant & Day in this way is that power is compromised when the prevalence of PD-L1+ is not 70%. In an all-comers trial, a design that uses the predictive information in PD-L1 score without assuming a prevalence would be preferable and to these ends, we developed BEBOP.

#### 9.3.2 BEBOP

The sample size of 60 patients was provisionally approved. We estimated the statistical operating performance in a broad simulation study using 12 scenarios and 60 patients.

In simulated trial iteration  $j$ , cohort membership probabilities  $\rho_j$  were randomly sampled from a Dirichlet distribution with parameter vector  $\hat{\rho} = (15.7, 21.8, 12.4, 20.7, 18.0, 11.4)$ .  $\hat{\rho}$  was calculated by splicing together the prevalence of (low, medium, high) PD-L1 scores observed in [1] in previously-untreated patients (0.315, 0.436, 0.249) and previously-treated patients (0.414, 0.359, 0.227), scaling each by 50% to reflect that we expect equal numbers of previously-untreated and –treated patients. Given a draw from this Dirichlet distribution, cohort memberships for iteration  $j$  were randomly sampled using a multinomial distribution with probabilities  $\rho_j$ . Summary statistics for the simulated cohort prevalences and cohort sizes are given in Table 5.

**Table 5 – Simulated cohort prevalences and sizes, based on 100,000 random draws using the described method.**

Cohort	$\rho_j$	Number of patients
	Mean (95% CI)	Mean (95% CI)
1	15.7% (9.3%, 23.4%)	9.4 (3, 17)

 BEBOP is the name originally given to this method by the authors at CRCTU. A referee pointed out that the design was a specialisation of the dose-finding design by Thall, Nguyen & Estey (TNE) (2008). Externally, the name P2TNE was adopted to reflect the heritage of the design, and the focus on phase-2. For simplicity, the name BEBOP is retained in internal documents,

2	21.8% (14.3%, 30.4%)	13.1 (6, 17)
3	12.4% (6.7%, 19.5%)	7.4 (2, 14)
4	20.7% (13.4%, 29.1%)	12.4 (5, 21)
5	18.0% (11.1%, 26.1%)	10.8 (4, 19)
6	11.4% (6.0%, 18.2%)	6.8 (2, 14)

To give measure to the benefit of information sharing in BEBOP, we also consider beta-binomial Bayesian conjugate models that assess the treatment in cohorts individually. With prior  $\pi \sim Beta(\alpha, \beta)$ , the posterior beliefs are  $\pi | q, m \sim Beta(\alpha + q, \beta + m - q)$  where  $m$  is the number of patients in a cohort and  $q$  is the number of events observed. Inferences are made on the posterior distribution. A Beta(0.4, 1.6) prior on the rates of efficacy and toxicity gives a prior mean event probability of 20% in each case, with a 95% credible interval of (0.0%, 80.5%). This prior is modestly informative, having an effective sample size of 2 patients.

For the purposes of measuring operating performance, using BEBOP and the beta-binomial models, we accepted the treatment at the end of each simulated trial if

$$\Pr(\pi_E(x_i, \theta) > 0.1 | X) > 0.7$$

and

$$\Pr(\pi_T(x_i, \theta) < 0.3 | X) > 0.9$$

Cohorts were evaluated individually. Table 6 shows operating characteristics of the described BEBOP design in 12 scenarios. The thresholds above were selected so that our BEBOP model under our regularising priors would approve with at least 80% probability in all cohorts in Scenario 1, and approve in Scenario 3 with no more than 5% probability.

In scenarios 1 to 4, the rates of efficacy and toxicity are uniform across the cohorts. Scenario 1 shows that if the true probability of efficacy is 30% and toxicity is 10%, we can expect BEBOP to approve the treatment with at least 85% probability in all cohorts. The cohorts have different approval probabilities because the average cohort sizes are different. A key benefit of the BEBOP design is the apportioning and sharing of information across cohorts via the Bayesian regression model. For instance, BEBOP will quite reliably approve the treatment in scenario 1 in cohorts 3 and 6, even though they each only receive approximately 7 patients who experience 2 efficacies. The high efficacy rate observed in other cohorts informs BEBOP. A statistical model that does not share information would not perform so well. The beta-binomial model would approve the treatment in cohort 3 in scenario 1 with probability only 50.5%. Using the described decision criteria with a cohort size of  $n=7$ , the beta-binomial model must observe at least  $q_E=4$  efficacy events to conclude that the treatment is efficacious. In contrast, BEBOP reliably approves the treatment in cohort 3 despite only observing 2.2 efficacy events in 7.4 patients, on average. BEBOP manages this because it observes 15.6 efficacy events in the residual 52.6 patients in the other five cohorts, on average. The high efficacy rate seen in the other cohorts helps BEBOP to approve the treatment in cohort 3 when it is truly effective, despite observing relatively few responses.

**Table 6 - Operating characteristics of the BEBOP model used in PePS2 over 12 simulated scenarios, reproduced from Brock et al [4].** Pr(Eff) and Pr(Tox) are the true probabilities of efficacy and toxicity. Odds denotes the ratio of odds of efficacy in patients that experience toxicity to those that do not. Odds=1 corresponds to no association; values less than one convey that efficacy is less likely when toxicity is observed; and vice-versa. N is the mean number of patients in a cohort; Eff and Tox the mean number of events. BEBOP is the probability that treatment is approved by the BEBOP model; Beta-Bin the probability it is approved by a beta-binomial model. 10,000 iterations were used in each scenario.

Scenario	Cohort	Pr(Eff)	Pr(Tox)	Odds	N	Eff	Tox	BEBOP	Beta-Bin	Scenario	Cohort	Pr(Eff)	Pr(Tox)	Odds	N	Eff	Tox	BEBOP	Beta-Bin
1	1	0.3	0.1	1.0	9.4	2.8	0.9	0.882	0.569	7	1	0.125	0.1	1.0	9.5	1.2	1.0	0.340	0.237
	2	0.3	0.1	1.0	13.1	3.9	1.3	0.903	0.679		2	0.185	0.1	1.0	13.1	2.4	1.3	0.607	0.466
	3	0.3	0.1	1.0	7.4	2.2	0.7	0.883	0.505		3	0.355	0.1	1.0	7.4	2.6	0.7	0.886	0.554
	4	0.3	0.1	1.0	12.4	3.7	1.3	0.893	0.658		4	0.100	0.1	1.0	12.4	1.2	1.2	0.248	0.197
	5	0.3	0.1	1.0	10.8	3.2	1.1	0.890	0.611		5	0.150	0.1	1.0	10.7	1.6	1.1	0.459	0.320
	6	0.3	0.1	1.0	6.8	2.0	0.7	0.872	0.489		6	0.300	0.1	1.0	6.9	2.1	0.7	0.776	0.489
2	1	0.3	0.3	1.0	9.5	2.8	2.8	0.178	0.123	8	1	0.167	0.1	1.0	9.5	1.6	0.9	0.457	0.337
	2	0.3	0.3	1.0	13.1	4.0	3.9	0.182	0.132		2	0.192	0.1	1.0	13.1	2.5	1.3	0.681	0.478
	3	0.3	0.3	1.0	7.5	2.2	2.2	0.178	0.132		3	0.500	0.1	1.0	7.4	3.7	0.7	0.979	0.630
	4	0.3	0.3	1.0	12.4	3.7	3.7	0.180	0.130		4	0.091	0.1	1.0	12.4	1.1	1.3	0.299	0.173
	5	0.3	0.3	1.0	10.8	3.2	3.2	0.180	0.130		5	0.156	0.1	1.0	10.8	1.7	1.1	0.493	0.340
	6	0.3	0.3	1.0	6.8	2.1	2.0	0.175	0.134		6	0.439	0.1	1.0	6.8	3.0	0.7	0.924	0.592
3	1	0.1	0.3	1.0	9.5	1.0	2.9	0.037	0.044	9	1	0.267	0.1	1.0	9.4	2.5	1.0	0.814	0.526
	2	0.1	0.3	1.0	13.0	1.3	3.9	0.036	0.036		2	0.292	0.1	1.0	13.0	3.8	1.3	0.921	0.681
	3	0.1	0.3	1.0	7.4	0.7	2.2	0.038	0.047		3	0.600	0.1	1.0	7.5	4.5	0.7	0.994	0.654
	4	0.1	0.3	1.0	12.4	1.2	3.7	0.030	0.038		4	0.191	0.1	1.0	12.4	2.4	1.3	0.737	0.471
	5	0.1	0.3	1.0	10.8	1.1	3.2	0.028	0.038		5	0.256	0.1	1.0	10.8	2.7	1.1	0.841	0.553
	6	0.1	0.3	1.0	6.9	0.7	2.0	0.033	0.047		6	0.539	0.1	1.0	6.9	3.7	0.7	0.981	0.621
4	1	0.3	0.1	0.2	9.4	2.8	0.9	0.885	0.588	10	1	0.267	0.3	1.0	9.4	2.5	2.8	0.162	0.124
	2	0.3	0.1	0.2	13.1	3.9	1.3	0.904	0.689		2	0.292	0.3	1.0	13.0	3.8	3.9	0.181	0.125
	3	0.3	0.1	0.2	7.5	2.3	0.7	0.893	0.524		3	0.600	0.3	1.0	7.5	4.5	2.2	0.195	0.175
	4	0.3	0.1	0.2	12.4	3.7	1.2	0.894	0.666		4	0.191	0.3	1.0	12.4	2.4	3.7	0.150	0.086
	5	0.3	0.1	0.2	10.9	3.3	1.1	0.894	0.632		5	0.256	0.3	1.0	10.8	2.8	3.3	0.170	0.112
	6	0.3	0.1	0.2	6.8	2.0	0.7	0.872	0.504		6	0.539	0.3	1.0	6.8	3.7	2.1	0.193	0.181
5	1	0.10	0.1	1.0	9.4	0.9	1.0	0.234	0.173	11	1	0.267	0.1	0.2	9.4	2.5	0.9	0.816	0.551
	2	0.15	0.1	1.0	13.1	2.0	1.3	0.460	0.366		2	0.292	0.1	0.2	13.2	3.8	1.4	0.919	0.683
	3	0.30	0.1	1.0	7.4	2.2	0.7	0.800	0.501		3	0.600	0.1	0.2	7.5	4.5	0.7	0.994	0.665
	4	0.10	0.1	1.0	12.5	1.2	1.3	0.232	0.194		4	0.191	0.1	0.2	12.4	2.4	1.3	0.738	0.479
	5	0.15	0.1	1.0	10.8	1.6	1.1	0.445	0.328		5	0.256	0.1	0.2	10.7	2.7	1.1	0.836	0.564
	6	0.30	0.1	1.0	6.8	2.0	0.7	0.758	0.478		6	0.539	0.1	0.2	6.8	3.7	0.7	0.983	0.629
6	1	0.10	0.3	1.0	9.5	0.9	2.8	0.042	0.040	12	1	0.267	0.1	5.0	9.4	2.5	0.9	0.813	0.495
	2	0.15	0.3	1.0	13.1	1.9	3.9	0.079	0.068		2	0.292	0.1	5.0	13.1	3.8	1.3	0.923	0.667
	3	0.30	0.3	1.0	7.4	2.2	2.2	0.133	0.134		3	0.600	0.1	5.0	7.5	4.5	0.7	0.993	0.650
	4	0.10	0.3	1.0	12.4	1.2	3.7	0.043	0.040		4	0.191	0.1	5.0	12.4	2.4	1.3	0.736	0.438
	5	0.15	0.3	1.0	10.8	1.6	3.3	0.079	0.064		5	0.256	0.1	5.0	10.8	2.7	1.1	0.837	0.537
	6	0.30	0.3	1.0	6.9	2.1	2.1	0.130	0.134		6	0.539	0.1	5.0	6.8	3.7	0.7	0.981	0.612

Scenario 2 shows that the design is materially less likely to approve the treatment when the toxicity rate is as high as 30%, despite the high efficacy rate. In this scenario, efficacy is high but toxicity is on the cusp of being acceptable. The design is very likely to reject the treatment when toxicity is as high as 30% and efficacy is as low as 10%, as seen in scenario 3. Despite leveraging information to approve the treatment with small cohort sizes when performance is good, BEBOP does not show a predisposition to approve the treatment when performance is poor. BEBOP is more likely than the cohort-specific beta-binomial models to reject the treatment in scenario 3 because it uses information from all 60 patients to estimate the toxicity rate.

Scenario 4 shows performance when efficacy events are highly negatively associated with toxicity. Here, the ability of patients to achieve efficacious outcomes are strongly hindered if they experience a toxicity event. In every other regard, the parameterisation of scenario 4 is the same as scenario 1. The performance of both methods are actually fractionally better in every cohort when events are associated.

Scenario 5 and 6 show performance when the efficacy probability improves with the rate of PD-L1 expression and pre-treatment status is uninformative (see Table 7). In scenario 5, efficacy is relatively poor in cohorts 1, 2, 4 and 5 but attractive in cohorts 3 and 6, and toxicity is low throughout. BEBOP approves the treatment in cohorts 3 and 6 with 75-80% probability, once again materially better than the beta-binomial models. In scenario 6, the odds of toxicity are much higher but the efficacy odds are the same. Both designs are now much less likely to approve the treatment.

Scenario 7 uses piecewise parallel efficacy curves, as shown in charts in Table 7. Translated to the probability scale, TN patients are 3-6% more likely to experience an efficacious outcome. Treatment is tolerable throughout. Once again, BEBOP is likely to correctly approve treatment in cohorts 3 and 6.

---

Other than the efficacy probabilities in cohorts 1-3, this scenario is otherwise the same as scenario 5. With the slight increase in efficacy probability, we expect the design to approve more often in cohort 3. It is pleasing, however, to see that the approval probability has slightly increased in cohort 6 too, even though it is unchanged. This is because the design has increased its expectations on the rate of efficacy in all high PD-L1 patients, based on the outcomes in the TN cohort.

Scenario 8 uses the efficacy rates in each cohort that [1] observed in their study, and a uniform toxicity probability of 10%. The notable aspect of this scenario is that there is an apparent interaction yielded by simultaneous low PD-L1 and pre-treated status so that the PD-L1-efficacy curves are not piecewise-parallel, as depicted in Table 7. BEBOP is overwhelmingly likely to approve treatment in cohorts 3 and 6 where efficacy is high. Interestingly, BEBOP is now more likely than not to approve treatment in cohort 2 as well, an improvement over the beta-binomial model of approximately 20%. It manages this, despite an average cohort size of 13.1 patients and efficacy rate only 9.2% above the critical value of 10%, because it leverages the outcomes observed in other cohorts.

In [1], stable disease was the best objective response level in 21.8% of patients. In our study, we have included stable disease in the efficacy event because it demonstrates disease containment, itself an achievement in PS2 NSCLC patients, thus we have reason to expect modestly higher efficacy rates than seen in [1]. That expectation is partly diminished because PS2 patients will be more frail than PS0 and PS1 patients and potentially less likely to achieve response. Scenario 9 uses the efficacy probabilities of Garon, increased in each instance by 10%. The objective here is to analyse how BEBOP performs when efficacy is high. Again, toxicity is left uniform at 10%. The design is now 90% likely to approve the treatment in three cohorts and at least 80% likely to approve in five out of six. In the remaining cohort, with efficacy probability 19.1%, BEBOP is over 70% likely to approve the treatment. This improvement over the approval rate in cohort 2 in scenario 8, despite the similar efficacy probability, comes from the sharing of information.

Scenario 10 is the same as scenario 9 with otherwise high probability of toxicity. Now, BEBOP is unlikely to approve the treatment, demonstrating the value of having simultaneous approval criteria for efficacy and toxicity.

Scenarios 11 and 12 are the same as scenario 9 with otherwise strong negative and positive association between efficacy and toxicity events. We see that the approval probabilities are largely unchanged.

The attractive operating characteristics of BEBOP confirm that 60 is an appropriate sample size in PePS2.

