**Table 9: Parameters for normal prior distributions for the elements of  $\theta$**

Parameter	Mean	Variance
$\alpha$	-2.2	4
$\beta$	-0.5	4
$\gamma$	-0.5	4
$\zeta$	-0.5	4
$\lambda$	-2.2	4
$\psi$	0	1

The EffTox software estimates the effective sample size of these priors to be equivalent to the outcomes of 1.32 patients, thus the priors may be considered to be weakly informative.

Given trial data  $\mathbf{X}$ , inferences on  $\theta$  and functions of  $\theta$ , such as  $\pi_E(\mathbf{x}, \theta)$  and  $\pi_T(\mathbf{x}, \theta)$ , are made using the posterior probability measure. This requires solving integrals of dimension equal to the number of elements in  $\theta$ . Generally, this is done numerically rather than analytically using software, described in the Statistical Analysis Plan (SAP).

Pembrolizumab will be considered successful in cohort  $i$  with the corresponding predictive vector  $\mathbf{x}_i$  taken from Table 8 if

$$\Pr(\pi_E(\mathbf{x}_i, \theta) > 0.1 | \mathbf{X}) > 0.7$$

and

$$\Pr(\pi_T(\mathbf{x}_i, \theta) < 0.3 | \mathbf{X}) > 0.9$$

That is, we want to be 70% certain a-posteriori that the efficacy rate exceeds 10% and 90% certain that the toxicity rate is less than 30%, to approve the treatment in a given cohort. Separate decisions will be made for each cohort. The hurdle rates for efficacy and toxicity were chosen for their clinical relevance by considering the equivalent rates associated with alternative treatments that these patients might receive. The certainty rates were chosen to give good operating performance with the identified sample size, described in the SAP.

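### SAP 9.3.2 sets no limit on approval when only one outcome fails, Table 6's Scenario 2 and most Scenario 10 approval rates exceed what the stated toxicity rule allows, and the four-event comparator figure is wrong

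*SAP*

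**What the plan says.** Protocol 13.2.1 and SAP 9.3.2 approve a cohort if Pr(efficacy > 0.1) > 0.7 and Pr(toxicity < 0.3) > 0.9. The protocol describes the second condition as being "90% certain that the toxicity rate is less than 30" per cent. Toxicity is one parameter shared by all six cohorts.

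SAP 9.3.2 says the cut-offs were selected so that the model would "approve with at least 80% probability in all cohorts in Scenario 1, and approve in Scenario 3 with no more than 5% probability". Scenario 1 has 30% efficacy and 10% toxicity; Scenario 3 has 10% efficacy and 30% toxicity.

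SAP 9.3.1 describes the original Bryant and Day calculation, which also produced 60 patients. There, "A significance level of 5% was selected as the acceptable chance of approving an unacceptably toxic drug as worthy of further investigation", with 30% as the unacceptable rate, and the design "would approve the treatment in the population if no more than 12 toxicities and at least 19 efficacies are observed".

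In its discussion of Table 6, SAP 9.3.2 says of Scenario 2 that "efficacy is high but toxicity is on the cusp of being acceptable". After describing Scenario 3 it adds that "BEBOP does not show a predisposition to approve the treatment when performance is poor" and that "BEBOP is more likely than the cohort-specific beta-binomial models to reject the treatment in scenario 3". On the comparator, it says that with seven patients the beta-binomial model must see at least four "efficacy events to conclude that the treatment is efficacious". The section ends by taking the operating characteristics as confirmation that 60 is an appropriate sample size.

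**The concern.** A treatment can be unsuitable because it is too toxic although active, or inactive although tolerable. The only stated ceiling on false approval applies where both faults are present, and there the two rules multiply together, so a small joint figure says little about either rule alone. Safety and tolerability is the first primary objective, and because toxicity is pooled, one mistaken toxicity pass carries to every cohort.

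A reader would therefore rely on Table 6 for the single-failure rates. If the printed values do not follow from the stated rule, that evidence for the sample size needs restating. The four-event statement matters less, but it sits in the paragraph that argues for sharing information and makes the comparator look stricter than it is.

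**Working it through.** **Inputs.** n = 60; the rule above; the SAP Table 3 priors, including a Normal(−2.2, variance 4) prior on the toxicity logit; the cohort sampling of SAP 9.3.2; Table 6, based on 10,000 iterations per scenario.

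**1. The plan's calibration.** A re-simulation of the six-parameter model (4,000 trials per scenario) gave these approval rates:

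| Scenario | Re-simulated | Table 6 |
|---|---|---|
| 1 | 0.888–0.927 | 0.872–0.903 |
| 3 | 0.025–0.032 | 0.028–0.038 |

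Both targets are met. Agreement is close but not exact: Scenario 1 comes out 1.3 to 2.7 points higher, cohort by cohort.

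**2. Single-failure rates printed in Table 6.**

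| Failure | Source | Approval |
|---|---|---|
| Toxicity 30%, efficacy above 10% | Scenario 2 | 0.175–0.182 |
| | Scenario 10 | 0.150–0.195 |
| | Scenario 6, cohorts 3 and 6 | 0.133, 0.130 |
| | Scenario 6, cohorts 2 and 5 | 0.079, 0.079 |
| Efficacy at or below 10%, toxicity 10% | Scenario 5, cohorts 1 and 4 | 0.234, 0.232 |
| | Scenario 7, cohort 4 | 0.248 |
| | Scenario 8, cohort 4 | 0.299 |

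**3. What the toxicity rule allows at 60 patients.** With t toxicities and p = expit(λ), the posterior is proportional to N(λ; −2.2, 4) × p^t (1 − p)^(60 − t). This sets the association term to zero. Integrating over p < 0.3, with exact binomial tails at a true rate of 30%:

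| t | Pr(toxicity < 0.3) | Passes 0.90? | P(X ≤ t) at 30% |
|---|---|---|---|
| 12 | 0.971 | yes | 0.057 |
| 13 | 0.944 | yes | 0.100 |
| 14 | 0.901 | at the margin | 0.162 |
| 15 | 0.840 | no | 0.244 |

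With the association term included and one common efficacy rate (3 to 36 efficacies, varying overlap with toxicity), t = 14 gives about 0.88 to 0.91 and t = 15 about 0.81 to 0.85. So 14 sometimes passes and 15 does not. The chance of passing at 30% toxicity lies between 0.100 and 0.162.

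**4. Comparison with the printed values.** Approval also requires the efficacy rule, so 0.162 is a ceiling. Scenario 1 approval is nearly the efficacy pass rate at 30% efficacy, because toxicity passes with probability 0.999 at a true 10%. The Scenario 2 ceiling is therefore about 0.162 × 0.872 = 0.141 to 0.162 × 0.903 = 0.146. Re-simulation gave 0.134 to 0.142, and other runs went as low as 0.125. The table prints 0.175 to 0.182. The simulation standard error at 0.162 is √(0.162 × 0.838 / 10,000) = 0.0037, so even 0.175 is 3.5 standard errors above the ceiling. In Scenario 10, cohorts 2, 3, 5 and 6 (0.181, 0.195, 0.170, 0.193) exceed it.

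The table's own ratios agree. Scenario 2 over Scenario 1 is 0.201 to 0.202, and Scenario 10 over Scenario 9 is 0.196 to 0.204, implying a toxicity pass rate near 0.20. Scenario 6 over Scenario 5 implies 0.166 to 0.185, although the toxicity rate and rule are the same.

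**5. Efficacy failing everywhere.** No scenario has 10% efficacy and 10% toxicity in all cohorts. Re-simulated, it gives about 0.16 to 0.20 per cohort (0.15 to 0.22 in a run with fewer posterior draws) and 0.58 to 0.59 for at least one cohort.

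**6. Four events or two.** With a Beta(0.4, 1.6) prior and q events in seven patients, the posterior is Beta(0.4 + q, 8.6 − q). Pr(rate > 0.1) is 0.612 at q = 1 and 0.896 at q = 2, so two events meet the 0.7 criterion. Averaged over the stated cohort sizes, the stated criterion gives 0.506 for cohort 3 in Scenario 1 against the printed 0.505. A four-event rule would give 0.143. The table is right on this and the sentence is wrong.

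**The case against.** The single-failure rates are printed, not hidden, and the SAP discusses Scenarios 2, 5 and 10 openly. A reader might infer that its reassurance about poor performance is contradicted by Table 6. That is too strong. The sentence follows directly on Scenario 3, and the next comparison names Scenario 3, where the table supports it: lower than the beta-binomial in five cohorts and equal in one. The wording is broader than its evidence, no more.

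A reader might also infer from the higher BEBOP approvals in most single-failure cells that sharing information makes the design lenient. The comparison is confounded. At 10% toxicity the small beta-binomial cohorts wrongly fail the toxicity rule 22 to 35% of the time, which lowers their joint approval. Their efficacy rule alone passes 24 to 26% of cohorts at 10% efficacy, much like BEBOP's 0.232 to 0.248. Only Scenario 8, cohort 4 (0.299 against 0.219 for the comparator's efficacy rule) shows an excess. With 10% efficacy and 10% toxicity throughout, the beta-binomial gives 0.162 to 0.200, so there is no clear excess.

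Finally, a reader might infer that the 0.90 cut-off breaches the 5% in SAP 9.3.1 and should be tightened. That 5% belongs to a superseded design, 30% is the boundary case (exact pass rates are at most 0.036 at 35% and 0.005 at 40%), and a stricter cut-off would reject tolerable treatment more often. The documents do not require one.

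None of this explains the printed 30% toxicity values or the four-event statement. Those stand.

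**Conclusion.** The point holds in limited form. The calibration limits false approval only where both outcomes fail. The printed Scenario 2 and most Scenario 10 approvals are not attainable under the stated rule: at most 0.162 at 30% toxicity, and about 0.13 to 0.14 in Scenario 2 by re-simulation, against a printed 0.175 to 0.195 in the worst cells. The four-event statement is an error of text.

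The ceiling rests on 60 patients, the stated toxicity prior, a common toxicity rate and the 0.90 cut-off. It does not depend on the re-simulation. The documents do not show why the table is higher. Its caption says the values were carried over from the methods paper, so a difference in settings or computation is possible, but that cannot be checked here. The corrected rates are more favourable to the design than the printed ones, and the decision rule is unaffected. This is a matter of correction and disclosure, worth considering rather than essential.

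**What to change.** 1. Re-run the 30% toxicity scenarios (2, 3, 6 and 10) under the stated rule and restate the BEBOP values in Table 6. State in SAP 9.3.2 that the 0.90 toxicity rule has roughly a 10 to 16% chance of passing at 30% toxicity with 60 patients, not the 5% of the superseded design in 9.3.1.
2. Add a scenario with 10% efficacy and 10% toxicity in all cohorts, reported per cohort and for at least one cohort. Limit the sentence about no predisposition to approve to the case where both outcomes are poor.
3. Correct the beta-binomial statement for seven patients from four efficacy events to two.

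The cost is a small amount of simulation and text editing in the SAP. No patients are added, and the decision rule in Protocol 13.2.1 stays as it is.
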